## 7.2 Subject Procedure

### Part 1

The purpose of the procedure in the Part 1 is to calculate the accuracy of Ligence Heart manual functions that are used to perform echocardiographic measurements comparing it with the accuracy of manual measurements performed with other CE marked state-of-the-art medical image viewers. Measurements made in Ligence Heart software will be compared with CE marked software “IntelliSpace Cardiovascular 5.1” (Phillips) and “EchoPAC” version 112 from GE Healthcare.

One cardiologist will perform 2D TTE measurements of each patient on each system 2 times. Time difference between repeated measures must be at least two days.

### Part 2

The purpose of the procedure in the Part 2 is to compare Ligence Heart automatic measurements accuracy and reliability with human cardiologists in real clinical setting.

Four physicians will make 2D TTE measurements of each subject study 2 times. Physicians cannot share thoughts or results between themselves. Time difference between repeated measures must be at least two days. Measurements of three physicians will be used in modeling and results of the 4th will be used as a validation with automated system.

During both parts, time used for the analysis of the 2D TTE images will be recorded. During manual 2D TTE image analysis, time it takes for physician to make measurements will be registered. Stopwatch starts when physician opens study in Ligence Heart and stops when all listed measurements are made. In the use case including automatic measurements, the time it takes for automatic system to make measurements and physician to correct/validate the results is registered.

Summary of the clinical investigation parts

#	Analysis	Purpose	TTE Examination Protocol	Measurements
Part 1	Manual Measurement Analysis	To calculate the accuracy of Ligence Heart manual functions that are used to perform echocardiographic measurements comparing it with the accuracy of manual measurements performed with other CE marked state-of-the-art medical image viewers.	One physician will make 2D TTE measurements of each patient on each system 2 times. Time difference between repeated measures must be at least two days.	
 
• AoS (PLA)
 
• RVB (A4CH)
 
• LVEDV (A4CH)
 
• LVEDV (A2CH)
 
• RVEDA (A4CH)
 
• RAA (A4CH)
 
• AV-Vmax
 

UAB Ligence	Clinical Investigation Report	2021-04-09
		Rev: 1.0

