## 12 Statistical Methods

### 12.1 Statistical Hypotheses

UAB Ligence	Clinical Investigation Report	2021-04-09
		Rev: 1.0

The following hypotheses will be tested with the statistical methods:

1. The manual functionalities of Ligence Heart provide equally accurate tools for echocardiography evaluation compared to other state of the art CE marked medical software.
2. Automatic functionalities of Ligence Heart software perform echocardiography image analysis with non-inferior accuracy compared to a cardiologist.
3. Automatic functionalities of Ligence Heart software perform echocardiography image analysis with lower intra-rater variability compared to a cardiologist.
4. Automatic functionalities produce measurement values faster than a cardiologist.

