#### 12.4.2 Data analysis

Two-way ANOVA will be employed to test for significant differences between measurements made in different medical imaging software. Interrater reliability coefficient and Pearson correlation coefficient will be calculated to check the level of interchangeability between software.

Intrater reliability coefficient interpretation

Interpretation	Value
Slight	0.00-0.20
Fair	0.21-0.40
Moderate	0.41-0.60
Substantial	0.61-0.80
Almost perfect	0.81-1.00

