LVESV4A	100.0 ± 0.0	100.0 ± 0.0		56	2	Yes
LVEDV2A	96.3 ± 5.03	100.0 ± 0.0	0.16	54	4	Yes

UAB Ligence	Clinical Investigation Report	2021-04-09
		Rev: 1.0

[figure not shown]
LVESV2A	96.3 ± 5.03	100.0 ± 0.0	0.16	54	4	Yes
RAA	94.44 ± 6.11	98.15 ± 3.59	0.31	54	4	Yes
RVB	98.18 ± 3.53	98.18 ± 3.53	1	55	3	Yes
RVM	100.0 ± 0.0	94.55 ± 6.0	0.08	55	3	Yes
RVOTPD	100.0 ± 0.0	100.0 ± 0.0		58	0	Yes
RVEDA	98.18 ± 3.53	100.0 ± 0.0	0.32	55	3	Yes
RVESA	98.18 ± 3.53	100.0 ± 0.0	0.32	55	3	Yes

*ORG - original rater group consisting of three board certified cardiologists; FC – fourth board certified cardiologist. \*P values for measurements that fall 100% in agreement in both groups are undefined. The “Pass” column specifies whether measurement accuracy is considered to be non-inferior. In order for the automated measurements to pass, a P value of > 0.05 or undefined is required which means that there is no significant difference in variation between Ligence Heart and FC measurements.*

UAB Ligence	Clinical Investigation Report	2021-04-09
		Rev: 1.0

[figure not shown]
Figure 1. Comparison of LigenceHeart and cardiologist measurements in agreement with the original rater group

**Figure 1.** The X axis represents the number of studies that were measured in agreement with ORG by Ligence Heart or FC. Each Y axis position represents a different measurement. 95% CIs are shown for Ligence Heart only. Ligence Heart 95% CI lower bound is at or above FC performance. ORG - original rater group. FC - fourth cardiologist.

[figure not shown]
UAB Ligence	Technical file	2021-04-09
		Rev: 1.0

Supplementary figure 1. Correlation of measurements between all raters

Electronic version of the document is valid, printed version of the document is not controlled. The document is stored at: Ligence Cloud storage unit. Internal company document.

UAB Ligence	Clinical Investigation Report	2021-04-09
		Rev: 1.0

[figure not shown]

**Supplementary figure 1.** Pearson correlation coefficients between all raters is shown. A value of -1 is assigned whenever the correlation is not calculated, either because it would be a duplicate or because it would compare measurements with the same rater and run. OR - original rater, R1 and R2 - run 1 and run 2, FC - fourth cardiologist, LH - Ligence Heart. Run 1 and run 2 refers to different repeats of the study by the same rater.

[figure not shown]

UAB Ligence	Clinical Investigation Report	2021-04-09
		Rev: 1.0

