## 16 Discussion and conclusions

### 16.1 Manual functionalities (Part 1)

Different types of manual measurements including area, distance and point measurements in B-mode and different spectral Doppler imaging modes have been tested and compared to two other CE marked medical image analysis platforms (EchoPAC by GE and Intellispace Cardiovascular by Philips). The measurement values obtained using the manual Ligence Heart functionalities did not show statistically significant variation when compared with other medical image analysis software. This proves that Ligence Heart can be used as medical image analysis software to analyze echocardiographic imaging data.

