### 16.2 Automatic functionalities (Part 2)

Due to the fact that echocardiography is prone to considerable inter- and intra-observer variability, it was important to perform comparison of the automatic measurements using data from multiple board certified cardiologists. The first three cardiologists established the acceptable intra- and inter-observer variation ranges while the fourth cardiologist and Ligence Heart were used as independent raters with accuracy calculated as the number of times measurements fell within acceptable variation range in the selected studies. Non-inferiority of automatic measurements accuracy to a cardiologist was established by conducting the t-test and assuring p-values are  $> 0.05$  which proves that any differences are non-significant. All of the measurements passed the required performance threshold, and for 7 out of 21 automatic measurements, both Ligence Heart and FC had full agreement with the ORG.

Conversely, Ligence Heart automatic functionalities did not return a value for at least one study in 11 measurements, however, there was a sufficient number of studies for all measurements where automatic analysis value was returned to ensure statistical power. The reason for no value being returned in a particular study has to do with the automatic predictions not passing quality thresholds which are employed in each step of the automatic functionalities (classification, cardiac phase or cycle detection and measurement prediction confidence). This ensures that a lower number of false values is provided to the user of the medical device and serves as a safety mechanism by reducing the number of potential false positive findings.

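### Part 2 declares non-inferiority from a non-significant difference test with no margin, so the 21 Pass entries do not support the claim

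*Protocol*

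**What the plan says.** Hypothesis 2 in Protocol section 12.1 is that the automatic functions "perform echocardiography image analysis with non-inferior accuracy compared to a cardiologist". Neither that section nor any other states how much worse the software may be and still count as non-inferior.

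The decision rule appears with the results. The Table 3 footnote in 15.2 explains that the Pass column marks a measurement as non-inferior, and adds: "In order for the automated measurements to pass, a P value of > 0.05 or undefined is required". Section 16.2 repeats the logic: "Non-inferiority of automatic measurements accuracy to a cardiologist was established by conducting the t-test and assuring p-values are" above 0.05. All 21 measurements are marked Pass. Section 16.2 closes by stating that non-inferior accuracy has been shown, and 16.3 that all expected performance has been proven.

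The benchmark is one reader, as section 7.2 planned: "Measurements of three physicians will be used in modeling and results of the 4th will be used as a validation with automated system".

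For Part 1, hypothesis 1 is equal accuracy. Section 12.4.2 plans a difference test ("Two-way ANOVA will be employed to test for significant differences between measurements made in different medical imaging software") plus reliability and Pearson coefficients. The Part 1 results section, also numbered 15.1, cites inter-software reliability above 0.8 and the absence of a significant difference. Section 16.1 mentions only that the measurements "did not show statistically significant variation when compared with other medical image analysis software", and its next sentence begins 'This proves'.

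**The concern.** A t-test of difference takes no difference as its null hypothesis. Failing to reject it can mean that the readers agree closely, or that there are too few studies to tell. A non-inferiority claim needs the opposite arrangement: the null is that the software is worse by at least a stated margin, and the interval for the difference must exclude that margin. Without a margin there is nothing to exclude.

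The rule also rewards weak data, because fewer studies or more scatter push the p-value up. Section 16.3 uses the result to conclude that a pre-market device meets its expected performance, so the inference carries the report's main claim about the automatic functions.

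**Working it through.** **Inputs.** Percentages, numbers of studies and p-values from Table 3 (15.2). Counts in agreement are percentage times N, rounded; for example LAD is 94.83% of 58 = 55, against 58 of 58.

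**1. Which test was run.** For 0/1 data with proportions a (Ligence Heart) and b (fourth cardiologist) on n studies each, the two-sample t statistic is t = (a - b) / sqrt{[a(1 - a) + b(1 - b)] / (n - 1)}, with 2n - 2 degrees of freedom.

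LAD: 0.9483 × 0.0517 = 0.0490; sqrt(0.0490 / 57) = 0.0293; t = -0.0517 / 0.0293 = -1.76 on 114 df, p = 0.081. Table 3 prints 0.08. All 14 defined p-values reproduce this way (LVPWd 0.156, AAo 0.319, RAA and LAV4A 0.313, RAMAD 0.562). The other seven are 100% against 100%, so p is undefined. The rule is therefore a plain unpaired test of difference.

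**2. What the rule does with less data.** With the fourth cardiologist at 100%, three Ligence Heart failures pass and four fail, both at n = 58 (four failures: p = 0.042) and at n = 20 (p = 0.036). So 3/58 = 5.2% failures pass at 58 studies, and 3/20 = 15% failures pass at 20.

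The chance of Pass for one measurement, from exact binomial enumeration with independent readers and assumed true agreement of 90% (Ligence Heart) and 98% (cardiologist):

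| n | Chance of Pass |
|---|---|
| 10 | 99% |
| 20 | 91% |
| 58 | 55% |
| 232 | 3% |

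**3. What the data allow.** The Newcombe lower limit is (a - b) - sqrt[(a - La)² + (Ub - b)²], where La and Ub are Wilson 95% limits. LAD: Wilson lower limit for 55/58 is 85.9%, upper limit for 58/58 is 100%, so -5.17 - (94.83 - 85.9) = -14.1. RAA: -3.70 - sqrt[(94.44 - 84.9)² + (99.7 - 98.15)²] = -13.4. Wald uses (a - b) - 1.96 × sqrt{[a(1 - a) + b(1 - b)] / n}.

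| Measurement | Agreement, Ligence Heart v fourth cardiologist (%) | Newcombe lower (points) | Wald lower (points) |
|---|---|---|---|
| LAD | 94.83 v 100 | -14.1 | -10.9 |
| RAA | 94.44 v 98.15 | -13.4 | -10.8 |
| LVEDV2A, LVESV2A | 96.30 v 100 | -12.5 | -8.7 |
| LVPWd | 96.55 v 100 | -11.7 | -8.1 |
| RAMAD | 96.30 v 98.15 | -10.8 | -8.0 |

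Six of 21 lie below -10 points by Newcombe, and two of 21 (LAD, RAA) by Wald. The 10-point line is an assumption used only to show scale.

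**4. Pairing.** Both readers read the same studies. Section 12.3 provides for ANOVA and the formulas given in Section 12, and none of those is a t-test. A paired t-test over every possible overlap of the disagreeing studies gives a smallest p of 0.083 (LAD and RVM), so pairing changes no Pass entry.

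**The case against.** **The minimal detectable change already sets a limit.** Section 12.5.2 compares each absolute difference with this quantity. That decides whether one reading agrees with the original raters. It puts no bound on how far Ligence Heart's agreement rate may fall below the cardiologist's. The performance threshold mentioned in 16.2 has no stated value other than the p-value rule.

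**The intervals overlap.** Section 15.2 notes that Ligence Heart's interval meets the cardiologist's result for every measurement. That is the absence of a demonstrated difference in another form. The Figure 1 caption goes further and puts the lower bound at or above the cardiologist's performance, but the LAD row gives 94.83 - 5.7 = 89.1 against 100.

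**The observed results are good.** This stands. A reader might infer that the software is inferior, or that poor devices usually pass. The documents support neither. The lowest Ligence Heart figure in Table 3 is 94.44%. The 55% applies to one measurement under assumed rates, not to a device that must pass 21.

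**A strict margin would be unfair.** This also stands. At 5 points even 58/58 against 58/58 fails, with a Newcombe limit of -6.2, so counting failures at that margin says little about the software.

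**Part 1 does not rest on p-values alone.** Correct for its results section, which leads with reliability of 89.30% to 99.26%. The coefficient in 12.4.1 has the software variance in its denominator, so a systematic offset lowers it. But 0.81 is an interpretation band in 12.4.2, not an acceptance limit, and no confidence intervals are given. Only 16.1 argues purely from non-significance.

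**One fixed benchmark reader.** This was planned in 7.2 and is not an error.

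**Conclusion.** Wrong as written for Part 2. The pass rule cannot establish non-inferiority, so the 21 Pass entries and the conclusions in 15.2, 16.2 and 16.3 do not follow. This does not depend on any assumed margin, and it is not something an unseen analysis plan could settle, because the document itself states the rule, applies it and concludes from it.

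The sizes shown are illustrative. They rest on counts rebuilt from rounded percentages, on readers treated as independent because the overlap of disagreements is not reported, and on assumed true rates and margin.

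Two lesser points also hold. The t-test is absent from Section 12 and ignores pairing, without altering any entry. For Part 1, the fault is confined to 16.1's claim of proof from non-significance and to the lack of intervals around the reliability figures.

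**What to change.** 1. In Table 3, 15.2, 16.2 and 16.3, remove the Pass rule and replace the words 'non-inferior' and 'proves' with a statement that no significant difference was detected.
2. For each of the 21 measurements, print the 95% interval for the paired difference in agreement, Ligence Heart minus fourth cardiologist, by a method suited to paired proportions near 100%.
3. Keep a non-inferiority claim only where the lower limit lies above minus a margin justified independently of these data. Label it post hoc if it was not pre-specified; a margin inserted into 12.1 now would not be pre-specified.
4. In 16.1, delete 'This proves' and report the mean difference from each comparator with a confidence interval, beside the reliability coefficient.

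The cost is rewording and a short re-analysis of the Table 3 agreement data and the Part 1 measurements. The downside is that some measurements can no longer be called non-inferior.

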## 15.2 Accuracy of automatic measurements (Part 2)

In order to establish the baseline inter- and intra-observer variability, the original rater group (ORG) consisting of three board certified cardiologists analyzed 58 2D TTE studies, repeating the measurements twice. This generated six values for each measurement in each study. The new rater group (NRG) consisting of a fourth cardiologist (FC) and Ligence Heart performed measurements in the same 58 studies. NRG performance was evaluated by calculating the number of measurements of each type that were in the limits of variation. FC was used as the performance benchmark for Ligence Heart.

There was no significant difference in variation between Ligence Heart and FC ( $p > 0.05$ ) and Ligence Heart had non-inferior accuracy to FC for all automatic measurements (**Table 3**). The lowest number of studies in agreement with ORG was 93.1% in RAA and 94.55% in RVM for Ligence Heart and FC, respectively. For AoS, STJ, IVSd, LVEDD, LVESD, LVESV4A and RVOTPD both FC and Ligence Heart were in agreement with ORG for 100% of studies. Ligence Heart discarded 2-4 studies in RAMAD, LAV4A, LVEDV4A, LVESV4A, LVEDV2A, LVESV2A, RVEDA and RVESA due to insufficient quality scores of automatic predictions (**Table 3**). Ligence Heart confidence interval for the number of studies in agreement with ORG intersected FC for all automatic measurements (**Figure 1**) and comparing each measurement between FC and Ligence Heart yielded a median Pearson correlation R 0.74 (IQR 0.59-0.83) (**Figure 2**).

Comparison of correlation between all raters and NRG measurement relation to ORG measurements is visualized in **Supplementary figures 1 and 2**, respectively.

**Table 3.** Comparison of Ligence Heart and cardiologist agreement with original rater group.

Measurement	Ligence Heart studies in agreement with ORG (95% CI)	FC studies in agreement with ORG (95% CI)	P-value*	N studies	N studies not passing confidence filter in Ligence Heart	Pass
RAMAD	96.3 ± 5.03	98.15 ± 3.59	0.56	54	4	Yes
AoA	98.28 ± 3.35	98.28 ± 3.35	1	58	0	Yes
AoS	100.0 ± 0.0	100.0 ± 0.0		58	0	Yes
STJ	100.0 ± 0.0	100.0 ± 0.0		58	0	Yes
AAo	98.28 ± 3.35	100.0 ± 0.0	0.32	58	0	Yes
LAD	94.83 ± 5.7	100.0 ± 0.0	0.08	58	0	Yes
LAV4A	98.21 ± 3.47	94.64 ± 5.9	0.31	56	2	Yes
IVSd	100.0 ± 0.0	100.0 ± 0.0		58	0	Yes
LVPWd	96.55 ± 4.7	100.0 ± 0.0	0.16	58	0	Yes
LVEDD	100.0 ± 0.0	100.0 ± 0.0		58	0	Yes
LVESD	100.0 ± 0.0	100.0 ± 0.0		58	0	Yes
LVEDV4A	98.21 ± 3.47	100.0 ± 0.0	0.32	56	2	Yes

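### Table 3's 95% intervals are Wald intervals that break down near 100% agreement, and the Figure 1 caption's lower-bound statement is contradicted by Table 3 in 12 of 21 rows

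*Protocol*

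**What the plan says.** Table 3 in section 15.2 gives each agreement percentage as an estimate plus or minus a half-width. The LH column heading begins "Ligence Heart studies in agreement with ORG (95% CI", and complete agreement is printed as 100.0 ± 0.0.

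Two sentences then compare LH with FC:

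- The Figure 1 caption: "Ligence Heart 95% CI lower bound is at or above FC performance". It makes no exception, and it notes that "95% CIs are shown for Ligence Heart only", so FC is a point value in the comparison.
- The running text: "Ligence Heart confidence interval for the number of studies in agreement with ORG intersected FC for all automatic measurements".

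The Table 3 footnote defines the Pass column by the p-value alone: above 0.05, or undefined because both raters are at 100%.

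**The concern.** The two sentences make different claims. A lower bound at or above FC would put the whole LH interval on the favourable side of FC. An interval that intersects FC says only that the two are not clearly apart. They can both hold in a row only where the lower bound equals FC.

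The intervals are also suspect. A 95% interval of zero width from 58 studies cannot be right, and an upper limit above 100% is impossible for a proportion.

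At stake is how the non-inferiority claim in sections 15.2 and 16.2 reads. A reader who trusts the caption would conclude that LH is at least as good as FC with 95% confidence throughout, and a reader of the 100.0 ± 0.0 rows would see no sampling uncertainty at all.

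**Working it through.** **Inputs.** From Table 3: percentage, half-width and number of studies for LH and FC in 21 rows. Counts are the percentage times N, rounded (LAD 55/58, RAA 51/54, AoS 58/58).

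**Step 1: reproduce the printed half-widths.** Formula: 100 × 1.96 × √(p(1−p)/n).

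- 57/58: 100 × 1.96 × √(0.9828 × 0.0172/58) = 3.35 (printed 3.35)
- LAD 55/58: 100 × 1.96 × √(0.9483 × 0.0517/58) = 5.70 (printed 5.7)
- RAA 51/54: 100 × 1.96 × √(0.9444 × 0.0556/54) = 6.11 (printed 6.11)
- 58/58: p(1−p) = 0, so 0.0 (printed 0.0)

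All 42 half-widths (LH and FC) match within 0.007 point. The document names no method; Wald is inferred from this match.

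**Step 2: behaviour of the LH intervals.** Eight rows have zero width: AoS, STJ, IVSd, LVEDD, LVESD, LVESV4A, RVM, RVOTPD. The other 13 have upper limits from 100.53 (LAD) to 101.71 (RVB, RVEDA, RVESA).

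**Step 3: test the caption.** LH lower bound = estimate − printed half-width. It is below FC in these 12 rows:

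| Measurement | LH lower bound | FC |
|---|---|---|
| RAMAD | 91.27 | 98.15 |
| AoA | 94.93 | 98.28 |
| AAo | 94.93 | 100 |
| LAD | 89.13 | 100 |
| LVPWd | 91.85 | 100 |
| LVEDV4A | 94.74 | 100 |
| LVEDV2A | 91.27 | 100 |
| LVESV2A | 91.27 | 100 |
| RAA | 88.33 | 98.15 |
| RVB | 94.65 | 98.18 |
| RVEDA | 94.65 | 100 |
| RVESA | 94.65 | 100 |

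The caption holds in 9 rows: the eight zero-width rows and LAV4A (94.74 against 94.64). Taking FC's lower limit as the comparator still leaves 10 failures. With the LH upper bound in place of the lower, the sentence would hold in all 21 rows.

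**Step 4: replace the intervals.**

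| Count | Printed lower | Wilson 95% | Clopper-Pearson 95% |
|---|---|---|---|
| 58/58 | 100 | 93.8 to 100 | 93.8 to 100 |
| LAD 55/58 | 89.1 | 85.9 to 98.2 | 85.6 to 98.9 |
| RAA 51/54 | 88.3 | 84.9 to 98.1 | 84.6 to 98.8 |

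Under either method the LH lower bound is below FC in all 21 rows.

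**Step 5: test the intersection sentence.** As printed it fails twice, both with LH above FC: RVM (100.0 ± 0.0 against 94.55) and LAV4A (94.74 to 101.68 against 94.64). In eight rows FC is 100% and LH is below 100%: AAo, LAD, LVPWd, LVEDV4A, LVEDV2A, LVESV2A, RVEDA, RVESA. A Wilson or exact interval with at least one miss ends below 100%, so LH reaches FC in those rows only because Wald overshoots.

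**Step 6: the 100%/100% rows.** For 58/58 against 58/58 the Wilson lower limit is 58/(58 + 1.96²) = 0.938. The Newcombe limits for the difference are ±√((1 − 0.938)² + 0²), about ±6.2 points, against a displayed uncertainty of zero.

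**RAA caveat.** Table 3 gives LH 94.44% (51/54), while the text of 15.2 gives 93.1%, which matches 54/58 = 93.10%. The text also leaves RAA out of its list of measurements with discarded studies, although Table 3 shows four. The RAA limits above use the tabulated count.

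**The case against.** The best defence is that none of this drives a decision. The Pass column rests on the p-value, section 16.2 says non-inferiority was established by a t-test, and the analysis planned in section 12.5.2 compares differences with the minimal detectable change (MDC) and the standard error of measurement (SEM), with no interval for a proportion. This stands: new intervals change no Pass entry under the stated rule. They are still the only uncertainty shown beside the claim, and they are wrong.

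A second defence is that the caption is a slip for the upper bound. That is plausible, and Figure 1 is not available to check. The printed sentence is still contradicted by the table, and an upper bound reaching FC would be a much weaker statement.

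A reader might go further in four ways that the documents do not support:

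- *The zero-width intervals cause the undefined p-values.* They do not. The p-value is undefined because both raters are at 100%. RVM has a zero-width LH interval and p = 0.08.
- *None of the 21 intervals is usable.* Too strong. In 13 rows the overshoot is 0.5 to 1.7 points, and the lower limit is too high by about 3.5 points for LAD and 3.7 for RAA. That is poor performance near 100%, not a total loss of information. The zero-width rows are the serious failure.
- *The caption carries the non-inferiority conclusion.* Sections 16.2 and 16.3 do not cite Figure 1.
- *LH is shown to be worse than FC.* Missing an FC point value of 100% does not show that, since FC's own 58/58 has a lower limit of 93.8%.

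**Conclusion.** The point holds as a reporting error to correct before Table 3 and Figure 1 are relied on. The caption is contradicted in 12 of 21 rows by plain subtraction, whatever interval method one prefers, and in all 21 with Wilson or exact limits. The intersection sentence is contradicted in two rows as printed and depends on Wald overshoot in eight more. Eight LH rows display zero uncertainty, where the exact lower limit for 58/58 is 93.8%.

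This rests on counts recovered by rounding Table 3's percentages, on the inference that the method is Wald, and, for RAA, on the tabulated 51/54. It does not show that non-inferiority is false. It shows that these intervals and sentences do not support it.

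**What to change.** - Recompute all Table 3 and Figure 1 intervals, for both LH and FC, with Wilson or Clopper-Pearson limits, and name the method.
- Delete or correct the caption sentence and the intersection sentence so that they agree with the table.
- Report the paired LH minus FC difference with a 95% interval in every row, including the seven 100%/100% rows, so that no row passes on an undefined p-value with no uncertainty shown. In the 16 rows where at least one rater is at 100%, the printed counts fix the paired table. RAMAD, AoA, LAV4A, RAA and RVB need the study-level data.
- Reconcile the RAA figure (93.1% in the text, 94.44% in Table 3) and the list of measurements with discarded studies.

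The cost is minutes of re-analysis on data already held. The price is wider, less favourable intervals.
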